3.3. Duration of Study

The day after Visit 1, subjects will begin a 14 day Screening Period to confirm their constipation status. Qualifying subjects will be randomized at Visit 2 and will begin a 6 month Treatment Period. Subjects will return for follow up clinic visits every 4 weeks during the Treatment Period.

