5.1. Adverse Event Definition and Reporting

An Adverse Event (AE) is any untoward medical occurrence associated with the use of a drug in humans, whether or not considered drug related. An AE can therefore be any unfavorable and unintended sign (inluding a clinically significant abnormal laboratory finding), symptom, or disease temporally associated with the use of a medicinal (investigational) product.

Adverse event collection will coincide with the subjects providing informed consent to participate in the study and will conclude with the end of study participation at Day 194 (2 week follow-up phone call). Diarrhea should be reported as an adverse event if a subject has more than 3 watery stools per day (Bristol Stool Rating = 7). Subjects with clinically significant laboratory results at Visit 8 which are classified by the Investigator as adverse events should return for a repeat blood draw. Subjects will be instructed to report promptly adverse events to the Investigator. The Investigator will record date/time of report, date/time of onset, description of the adverse event, severity of adverse event, action(s) taken regarding study participation, duration of adverse event, and the Investigator's assessment of relationship of adverse event to study treatment.

The Investigator should assess the severity of each adverse event using the following categories:

Grade	Severity	Description	
1	Mild	Barely noticeable, does not influence functioning	
	MIIId	Causing no limitations of usual activities	
2	Moderate	Makes participant uncomfortable, influences functioning	
	Moderate	Causing some limitations of usual activities	
3		Severe discomfort, treatment needed	
	Severe	Severe and undesirable, causing inability to carry out usual	
		Activities	
4	Life	Immediate risk of death	
	threatening	Life threatening or disabling	
5	Fatal	Causes death of the participant	

The Investigator should assess the relationship to study drug for each adverse event using the following categories:

Categories of Attribution:	Description
UNRELATED	There is no evidence of any causal relationship.
POSSIBLE	There is some evidence to suggest a causal relationship (e.g., the event occurred within a reasonable time after administration of the trial medication). However, the influence of other factors may have contributed to the event (e.g., the patient's clinical condition, other concomitant events).

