PROBABLE	There is evidence to suggest a causal relationship, and the influence of other factors is unlikely .
DEFINITE	There is clear evidence to suggest a causal relationship, and other possible contributing factors can be ruled out .

In published Phase 3 studies, adverse events associated with BLI400 administered at doses required for effective treatment of constipation included flatulence, nausea, vomiting, abdominal cramping or pain and bloating. These adverse reactions were transient and subsided rapidly upon dose adjustment or cessation.

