Analysis of safety will be performed using the modified Intent-to-Treat population (see Section 9.4). Safety analyses may also be presented by age, gender and racial subgroup.

Adverse Events

Adverse Events will be coded using the MedDRA classification to provide a preferred term and primary system organ class for each event. Proportions of subjects with adverse events will be presented by treatment group. Tables of AEs will be presented by system organ class and preferred term, and include overall totals for AEs within each system organ class. Counting will be done by subject and not by event. A table of counts and percentages will also be made of those subjects with SAEs or AEs which led to withdrawal from the study.

Treatment-emergent AEs are defined as adverse events that had an onset day and time on or after the day and time of the first dose of study drug up to 14 days after the last dose of

study medication. Adverse Events having missing onset dates will be considered as treatment-emergent.

The difference in adverse event rates between study groups will be tested by Chi-Square or Fisher's exact test with 95% confidence intervals. Adverse events will be presented for the overall Treatment Period.

Laboratory Parameters

Summary statistics (i.e., mean, minimum, maximum, standard deviation, and number of subjects) will be presented for each treatment group for each laboratory parameter at each visit. When calculating the summary statistics only, the last observation within a visit window will be used if there are multiple observations. Changes from Visit 1 (Screening) will be presented in a similar format. An additional listing will be provided of those subjects who have clinically significant laboratory values. The data will also be presented as shift tables, and clinically significant abnormalities will be examined.

Results of laboratory tests for the change from Visit 1 (Screening) and group differences will be tested using ANOVA.

Vital Signs

Summary statistics (i.e., mean, minimum, maximum, standard deviation, and number of subjects) will be presented for each treatment group for each vital sign at each visit. When calculating the summary statistics only, the last observation within a visit window will be used if there are multiple observations. The data will also be presented as shift tables and clinically significant abnormalities will be examined.

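### Treatment-emergent AEs are defined by onset alone, so a screening complaint that worsens on study drug is left out unless a site happens to log the worsening as a new event

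*Combined protocol and SAP*

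**What the plan says.** Section 9.3.3 (Safety Analyses, Adverse Events) sets the lower bound of the treatment-emergent window by onset: "Treatment-emergent AEs are defined as adverse events that had an onset day and time on or after the day and time" of the first dose. The upper bound is "up to 14 days after the last dose of" study medication. One other route in is given: "Adverse Events having missing onset dates will be considered as treatment-emergent". Counting in the AE tables is by subject.

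Section 5.1 starts collection well before dosing: "Adverse event collection will coincide with the subjects providing informed consent to participate in the study". Section 3.3 places the screening window between Visit 1 and randomization: "subjects will begin a 14 day Screening Period to confirm their constipation status". Section 4.2.1 has sites ask about AEs at Visit 2, and Section 4.3.2 puts the first dose on the day after randomization.

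For each AE, Section 5.1 specifies the content of the record: "The Investigator will record date/time of report, date/time of onset, description of the adverse event, severity of adverse event", followed by action taken, duration and relationship to treatment. It does not say what to do when an event already on record becomes more severe. The same section lists the expected drug effects as "flatulence, nausea, vomiting, abdominal cramping or pain and bloating".

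The Clinical Protocol Summary Sheet names treatment-emergent AEs, with laboratory and ECG data, as the basis of the safety assessment.

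**The concern.** A treatment-emergent definition should separate what was there before treatment from what appeared or got worse on it. This one captures only what appeared. The omission matters here because the expected effects of the drug are GI symptoms that constipated subjects can already have before dosing. The Summary Sheet itself lists bloating and abdominal discomfort among the symptoms to be rated. The design then elicits pre-dose complaints and gives them a pre-dose onset.

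At stake are the treatment-emergent counts for individual GI preferred terms, and the comparison between arms where AE rates are tested on the treatment-emergent set. If worsening differs by arm, the events left out differ by arm too.

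The missing-onset rule errs the other way. It has no exception for an event known to have stopped before the first dose, so an event that cannot be treatment-emergent would be counted.

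**Working it through.** **Step 1: apply the rule as written.** The plan states no figure on this point, so the first check is of the text.

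| Event | Onset relative to first dose | Treatment-emergent under 9.3.3? |
|---|---|---|
| Nausea starts in week 2 of treatment | after | yes |
| Mild bloating starts in screening, unchanged on drug | before | no (correct) |
| Mild bloating starts in screening, severe on drug, one record kept | before | no (misclassified) |
| Same, but the site opens a new record at worsening | after, for the new record | yes |
| Onset missing, stop date before first dose | unknown, but it ended before | yes (misclassified) |

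The Summary Sheet and Sections 5.1, 6 and 9.3.3 were checked for a worsening clause. None has one. Rows 3 and 4 are the same clinical event. Which row applies depends on site habit, because Section 5.1 gives no instruction.

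**Step 2: size.** The documents give no rate of screening AEs and no rate of worsening, so the inputs below are assumptions, apart from the arm size.

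- n = 300 per arm (Section 9.1).
- s = share of subjects with a GI complaint recorded as an AE in screening: 5-10%.
- wB = share of those whose complaint worsens on BLI400: 30-50%.
- wP = the same on placebo: 10-20%.

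Subjects left out per arm = n × s × w:

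- BLI400: 300 × 0.05 × 0.30 = 4.5, up to 300 × 0.10 × 0.50 = 15.
- Placebo: 300 × 0.05 × 0.10 = 1.5, up to 300 × 0.10 × 0.20 = 6.

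Arm difference hidden = s × (wB − wP), in percentage points:

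| s | wB 30%, wP 20% | wB 30%, wP 10% | wB 50%, wP 20% | wB 50%, wP 10% |
|---|---|---|---|---|
| 5% | 0.5 | 1.0 | 1.5 | 2.0 |
| 10% | 1.0 | 2.0 | 3.0 | 4.0 |

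Over all combinations the range is 0.5 to 4 points, or 1.5 to 12 subjects out of 300. Pairing only low with low (0.05 × 0.20 = 1 point) and high with high (0.10 × 0.30 = 3 points) would give too narrow a range.

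**Step 3: what the sign depends on.** The sign is that of wB − wP. If the two are equal, no arm difference is hidden, but each arm's count is still too low by s × w. If worsening is more common on placebo, the sign reverses.

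**Step 4: which totals move.** Because counting is by subject, a subject missed for one term may already count in the system-organ-class or any-AE total through another event. The range in Step 2 is therefore most relevant to individual terms and is an upper guide for the totals.

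**The case against.** Several points on the other side are sound, and they limit what can be claimed.

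- **That such events never enter the table.** A reader might infer this, but the documents do not support it. Section 5.1 defines an AE broadly and does not forbid logging a worsening as a new event. Section 9.3.3 also does not say which AE tables or tests are restricted to treatment-emergent events, and SAEs and AEs leading to withdrawal have their own table with no stated onset limit. The most consequential worsening may appear there. Milder worsening has no assured place in the treatment-emergent set.
- **That the safety comparison is biased toward no difference.** This needs more worsening on BLI400, which is an assumption. The Introduction presents the product as relieving constipation symptoms, so screening complaints could worsen more on placebo.
- **That every subject comes off usual laxatives before dosing.** Exclusion criterion 6 concerns subjects who take laxatives. The documents do not say that all do, and rescue bisacodyl is dispensed for screening (Section 4.1).
- **A narrow pool.** Only recorded AEs that begin between consent and first dose and are still ongoing are affected. Long-standing complaints may be captured as medical history at Visit 1. Diarrhea is little exposed: Section 4.2 bars any spontaneous bowel movement rated Bristol 7 in screening, and Section 9.3.2 counts diarrhea episodes weekly.
- **A possible backstop.** The Summary Sheet lists weekly bloating and discomfort ratings. However, the diary descriptions (Sections 4.1.3 and 4.3.1) and the secondary endpoints in Section 9.3.2 do not repeat them, so it cannot be relied on.
- **Missing onset.** Section 5.1 requires an onset date, so missing ones should be uncommon, and counting them is a conservative convention applied to both arms. The absence of a stop-date exception is a small error, but a real one.
- **A later analysis plan.** Section 9.4.3 refers to a statistical analysis plan, and no separate text of one is available here. It could add a worsening clause. It could not recover the date of a worsening that sites were never asked to record.

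These points reduce the reach and make the size uncertain. They do not supply the missing clause.

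**Conclusion.** The point holds in limited form. Section 9.3.3 states a rule that misclassifies screening-onset events that worsen on study drug, and Section 5.1 leaves it to each site whether the worsening gets its own record. Treatment-emergent counts for individual GI terms can be understated as a result.

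The size cannot be derived from the documents. Under the stated assumptions it is roughly 0.5 to 4 percentage points of arm difference for GI complaints, and less for any-AE totals. Shrinkage of the difference rests on the further assumption that worsening is more common on BLI400. The primary efficacy endpoint is not touched. The definition should be corrected because it governs a named safety measure, the change is small, and the worsening date may be lost if sites are not told to record it.

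**What to change.** In Section 9.3.3, define a treatment-emergent AE as one with onset at or after the first dose, or with earlier onset and an increase in severity or seriousness after the first dose, in either case up to 14 days after the last dose. Treat an AE with missing onset as treatment-emergent unless its stop date precedes the first dose.

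In Section 5.1, instruct sites to record a worsening as a new AE with its own onset date. Both parts are needed, because the analysis rule can be applied only if the time of worsening is in the data. Counting by subject means the extra record does not count a subject twice within a term.

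The cost is a short addition to each of the two sections and an eCRF completion note. Reported treatment-emergent rates will rise slightly. Treatment, visits and sample size do not change.

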3.5.2. Exclusion Criteria

Subjects who meet any of the following criteria will be excluded from the study:

- 1. Report loose (mushy) or water stools in the absence of laxative use for more than 25% of BMs during the 12 weeks before Visit 1
- 2. Meet the Rome II criteria for Irritable Bowel Syndrome: reports abdominal discomfort or pain that has two or more of the following three features for at least 12 weeks, which need not be consecutive, in the 12 months before Visit 1:
 - Relieved with defecation
 - Onset associated with a change in frequency of stool
 - Onset associated with a change in form (appearance of stool)
- 3. Subjects with known or suspected ileus, gastrointestinal obstruction, gastric retention, bowel perforation, toxic colitis, toxic megacolon
- 4. Subjects who have had major surgery 30 days before Visit 1; appendectomy or cholecystectomy 60 days before Visit 1; abdominal, pelvic, or retroperitoneal surgery 6 months before Visit 1; bariatric surgery or surgery to remove a segment of the GI tract at any time before Visit 1
- 5. Subjects with hypothyroidism that is being treated and for which the dose of thyroid hormone has not been stable for at least 6 weeks at the time of Visit 1
- 6. Subjects taking laxatives, enemas or prokinetic agents that refuse to discontinue these treatments from Visit 1 until after completion of the study
- 7. Subjects who are pregnant or lactating, or intend to become pregnant during the study
- 8. Subjects of childbearing potential who refuse a pregnancy test
- 9. Subjects who are allergic to any study medication component (lactitol or maltodextrin)
- 10. Subjects taking narcotic analgesics or other medications known to cause constipation
- 11. Subjects with clinically significant cardiac abnormalities identified at the Visit 1 ECG
- 12. Subjects with clinically significant laboratory abnormalities, deemed as a potential safety issue by the Investigator
- 13. Subjects who, in the opinion of the Investigator, should not be included in the study for any reason, including inability to follow study procedures
- 14. Subjects who have participated in an investigational clinical, surgical, drug, or device study within the past 30 days
- 15. Subjects with an active history of drug or alcohol abuse
- 16. Subjects have been hospitalized for a psychiatric condition or have made a suicide attempt during the 2 years before Visit 1
- 17. Subjects who withdraw consent at any time prior to completion of Visit 1 procedures

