4.1. Visit 1: Screening

At the screening visit, the following procedures will be undertaken:

- Subject is fully informed about the study and gives written agreement to study participation in the form of a signed informed consent form (refer to Section 4.1.1) and assign a subject number
- Assess eligibility (refer to inclusion/exclusion criteria)
- Review of medications
- Medical history including history of constipation (ROME criteria see inclusion #2)
- Physical examination
- Vital signs: including assessment of orthostatic hypotension (while seated and after standing for a minimum of 2 minutes) including height and bodyweight, pulse and temperature
- A 12-lead ECG will be performed by qualified, trained site personnel. ECG output must be reviewed by a physician investigator. Any clinically significant cardiac abnormalities identified on the ECG should disqualify a subject. Data from the ECG will be collected in the eCRF.
- Blood and urine samples will be collected for testing at a central laboratory, as shown below.

Chemistry: alkaline phosphatase, ALT, anion gap, AST, bicarbonate, blood urea nitrogen (BUN), calcium, chloride, creatine kinase (CK), creatinine, eGFR, GGT, HCG, inorganic phosphate, magnesium, osmolality, potassium, sodium, uric acid. CK-MB will be tested in samples where the CK value is greater than 2.5 times the upper normal limit.

Hematology: hematocrit, hemoglobin, platelets count, red blood cell count, white blood cell count (and differentials)

Pharmacokinetic (PK) Sampling: lactitol

Urinalysis: including electrolytes (sodium, potassium, magnesium, calcium), microscopic analysis, urine osmolality

Subjects with clinically significant laboratory abnormalities, deemed as a potential safety issue by the Investigator, may be discontinued at the Investigator's discretion.

- Provide the subject an electronic diary and review instructions with the subject in detail to ensure full understanding (refer to Section 4.1.3).
- Dispense rescue bisacodyl. Subjects will be allowed to take 5 10mg of bisacodyl if they are experiencing severe discomfort due to their constipation, or have not had a BM in 4 days.
- Instruct subject to maintain their normal dietary habits during study participation.
- Schedule the next study visit to occur after 14 full screening days.

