9. DATA ANALYSIS

9.1. Sample Size

Six hundred subjects will be randomly assigned to BLI400 (21 g/day dose) or placebo in a ratio of 1:1 (300 BLI400, 300 placebo). The definition of a weekly responder is based on weekly assessments of complete spontaneous bowel movements (CSBMs).

Based on data from a previous laxative study (Lembo et al, 2011) utilizing this primary efficacy variable (percent of subjects who are responders), it is anticipated that approximately 20% of subjects would be classified as responders in the BLI400 arm, with a placebo response up to 10%. The proposed study size will have approximately 90% power to detect a difference of 10% between the active and placebo groups at a two-sided significance level of 0.05.

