ECG variables will be tabulated and presented for data collected at each visit. Data will be tabulated and summarized with descriptive statistics (N, mean, SD, CV%, SEM, minimum, and maximum) for each of the ECG variables. The differences in ECG variables between Visit 1 (Screening) and Visit 8 will be tested using ANOVA.

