9.4.3. Per-Protocol Population

The per protocol (PP) population will consist of all subjects in the mITT population who have not violated the study eligibility criteria and have not deviated significantly from the protocol during the course of the study. Any efficacy analyses from this population will be considered as supportive to the ITT and mITT analyses. Reasons for exclusion from the PP population will be defined prospectively in the statistical analysis plan and prior to unblinding of the data.

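### Laboratory and ECG changes from Visit 1 are tested by ANOVA with no Visit 1 covariate named: unbiased, but never more precise than ANCOVA on values already collected

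*Combined protocol and SAP*

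**What the plan says.** Section 9.3.3 (Safety Analyses), under Laboratory Parameters: "Results of laboratory tests for the change from Visit 1 (Screening) and group differences will be tested using ANOVA". The ECG paragraph that closes the section: "The differences in ECG variables between Visit 1 (Screening) and Visit 8 will be tested using ANOVA". The laboratory sentence mentions group differences; the ECG sentence does not. Neither lists model terms, and ANCOVA appears nowhere in the document.

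The Visit 1 values exist for every randomized subject under the plan. Section 4.1 says of the laboratory samples "Blood and urine samples will be collected for testing at a central laboratory, as shown below", and of the ECG "Data from the ECG will be collected in the eCRF". Randomization follows at Visit 2 (section 4.2.1). The table in section 4.4 schedules laboratory samples again at Visits 3 to 8 and the ECG again at Visit 8 only.

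Section 9.3.3 also plans summary statistics, shift tables and a review of clinically significant abnormalities for the laboratory data, with a listing of the subjects concerned.

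Section 9.4.3 refers to a further document: "Reasons for exclusion from the PP population will be defined prospectively in the statistical analysis plan and prior to unblinding of the data". No separate text of that plan is supplied.

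**The concern.** As written, the Visit 1 value enters only by subtraction. Subtracting fixes its coefficient at 1, whereas ANCOVA estimates the coefficient from the data. Unless the true coefficient is 1, subtraction leaves avoidable noise in the between-arm comparison.

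The objective in section 2 is safety as well as efficacy against placebo, and the summary sheet names laboratory and ECG data among the three safety sources. For tests meant to pick up harm, lost precision makes a real difference easier to miss.

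The ECG sentence adds a question of wording. It can be read as a comparison of two visits within subjects, which would not answer a question about BLI400 against placebo.

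**Working it through.** **Inputs from the documents.** 1:1 allocation with 300 per arm (section 9.1); laboratory tests possible at Visits 3 to 8, ECG at Visit 8 (section 4.4). The two-sided 0.05 level is stated in section 9.1 for the primary endpoint only and is borrowed here.

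**Assumptions.** The documents give neither the correlation r between Visit 1 and the later visit nor the SDs (s0 at Visit 1, s1 at the post-baseline visit tested). I take r = 0.3, 0.5, 0.7 and 0.9, first with s0 = s1 and then with s0/s1 = 0.8. The second case is plausible because eligibility screens out extremes at Visit 1: exclusion 11 removes "Subjects with clinically significant cardiac abnormalities identified at the Visit 1 ECG", and exclusion 12 does the like for laboratory abnormalities.

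**The plan's own figure.** No power or precision is stated for the laboratory or ECG tests. The only power figure, about 90% for the primary endpoint (20% against 10%, 300 per arm), recomputes as 93.1%, or 92.0% with a continuity correction. It does not bear on this point.

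**Formulas.**
- Per-subject variance of the change: s0² + s1² − 2·r·s0·s1.
- Per-subject residual variance under ANCOVA: s1²(1 − r²).
- Difference: (s0 − r·s1)², never negative, and zero when r = s0/s1.
- Variance of the between-arm difference: 2/n times the per-subject variance, so its excess is (2/n)(s0 − r·s1)². Example: equal SDs, r = 0.5, n = 300, s1 = 1 gives (2/300) × 0.25 = 0.00167, from 0.00667 (ANOVA) against 0.00500 (ANCOVA).
- ANCOVA power where ANOVA has 80%: Φ(2.802 × SE ratio − 1.960), where SE ratio is ANOVA over ANCOVA.

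**Results** (s1 = 1):

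| s0/s1 | r | Change variance | ANCOVA variance | SE ratio | ANCOVA power |
|---|---|---|---|---|---|
| 1.0 | 0.3 | 1.40 | 0.91 | 1.240 | 93.5% |
| 1.0 | 0.5 | 1.00 | 0.75 | 1.155 | 89.9% |
| 1.0 | 0.7 | 0.60 | 0.51 | 1.085 | 86.0% |
| 1.0 | 0.9 | 0.20 | 0.19 | 1.026 | 82.0% |
| 0.8 | 0.3 | 1.16 | 0.91 | 1.129 | 88.6% |
| 0.8 | 0.5 | 0.84 | 0.75 | 1.058 | 84.3% |
| 0.8 | 0.7 | 0.52 | 0.51 | 1.010 | 80.8% |
| 0.8 | 0.8 | 0.36 | 0.36 | 1.000 | 80.0% |
| 0.8 | 0.9 | 0.20 | 0.19 | 1.026 | 82.0% |

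With equal SDs the variance ratio, ANCOVA over ANOVA, is (1 + r)/2. ANCOVA would therefore match ANOVA on 300 per arm with about 195, 225, 255 or 285 per arm.

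The difference detectable with 80% power is 2.802 × √(2/n) × √(per-subject variance). With equal SDs and r in the same order, 300 per arm gives 0.271, 0.229, 0.177 and 0.102 SD for ANOVA, against 0.218, 0.198, 0.163 and 0.100 SD for ANCOVA.

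**Simulation check.** With 4,000 trials, 300 per arm, equal SDs and a true difference of 0.20 SD, both methods gave mean estimates of 0.197 to 0.199. The variance ratios were 0.656, 0.744 and 0.864 at r = 0.3, 0.5 and 0.7, against 0.65, 0.75 and 0.85 from the formula.

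**Chance imbalance.** With equal SDs, a Visit 1 imbalance of 0.1 SD between arms shifts the change-score estimate by (1 − r) × 0.1 SD: 0.07, 0.05, 0.03 or 0.01 SD at the four values of r. ANCOVA adjusts for it.

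**The case against.** The strongest reply is that nothing here is an error. ANOVA of change is a valid test, it is named in advance, and these tests are neither powered nor confirmatory. Laboratory safety is also judged from shift tables and a listing of clinically significant values, which a covariate leaves untouched. All of that stands, and it puts the point at the lowest severity.

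The reply that the absence of a covariate rests on silence also stands in part. The plan cited in section 9.4.3 could specify one, so the point concerns the method as named in the text supplied.

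It is also fair that the gain is assumed rather than known. It shrinks when the Visit 1 SD is the smaller one and vanishes when r = s0/s1. What does not follow is that ANCOVA might do worse. With 1:1 allocation it loses no precision in large samples, even if the baseline slope differs by arm, and the finite-sample cost is one degree of freedom among roughly 600.

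A reader might also infer that the last-in-window rule hides abnormal results when a Visit 8 laboratory abnormality leads to a repeat draw under section 5.1. The documents do not support that. The rule is limited in its own words: "When calculating the summary statistics only, the last observation within a visit window will be used if there are multiple observations". Shift tables and the listing fall outside it, and no timing for the repeat draw or analysis window is given from which an effect could be shown.

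**Conclusion.** The point holds as an efficiency and wording matter. Under the equal-SD assumption, leaving out the Visit 1 covariate inflates the standard error by 2.6% to 24.0% for r from 0.9 down to 0.3. With the Visit 1 SD at 0.8 of the later SD, the inflation runs from nil to 12.9%. Both ranges rest on assumed values of r and of the SD ratio.

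A reader might infer that the planned comparisons are biased. They are not: under randomization with complete data both methods are unbiased, and dropout before later visits could bias either. Nor does the point reach the primary endpoint, its CMH test or the sample size.

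The ECG wording does not depend on any assumed value. Section 9.3.3 does not say whether the arms or the visits are compared, and the text should settle this. The laboratory sentence likewise does not say which of Visits 3 to 8 are tested.

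**What to change.** In section 9.3.3, or in the statistical analysis plan before unblinding:
- Compare BLI400 with placebo by ANCOVA of the post-baseline value (or the change), with treatment and the Visit 1 value in the model. Apply it at each laboratory visit to be tested, naming those visits, and at Visit 8 for ECG variables.
- Word the ECG test as a between-arm comparison of the Visit 1 to Visit 8 change.
- Keep the descriptive change tables, shift tables and listings as planned.

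The cost is a few words and one model term in the programming. There are no new data, visits or procedures, since the Visit 1 values are already collected.
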